DoR refers to the time when complete response (CR) or partial response (PR) is first observed until the time of progressed disease (PD) or death for the subjects whose best overall response is complete response (CR) or partial response (PR). If the subject did not have an event of PD or death, then DoR will be the time of last tumor assessment.

DoR will be listed.

Summaries of DoR will include summary statistics of duration, the number and the associated percentage of patients whose DOR is >3, >6, >9 and >12 months for Part A and Part B and overall (Part A and B). In case of sufficient responders, the median of DOR (calculated based on Kaplan-Meier) and 95% confidence interval of median time will also be summarized.

h) Tumour Volume (mL)

Tumour Volume (mL) is measured for each lesion at each scheduled visit by independent central review using RECIST (v1.1) and CCI. The sum of the tumour volume (mL) per visit will be computed and descriptive statistics of tumour volume, change in tumour volume and percentage change in tumour volume will be generated at each scheduled visit on the ITT and PP sets.

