3.2.4 Missing data and outliers

3.2.4.1 Missing data

a) Efficacy endpoints

When tumour assessment visits are completely missing, rules from FDA Guidance “Clinical Trial Endpoints for the Approval of Cancer Drugs and Biologics” [4] will be implemented as described in section 3.2.3.

Any missing QoL data (EORTC QLQ C30 and QLQ GI.NET21 questionnaires) will be handled as described in section 3.2.3.

b) Safety endpoints

If a value required a retest (for laboratory values, vital signs), the closest non-missing value to the scheduled visit will be used in the summary tables.

If there is a significant number of missing values for a subject (or if there is confirmed data appearing spurious), a decision will be made following consultation with the sponsor regarding the handling of these data in summaries. This decision will be made during the Data Review Meeting and documented.

Any repeat or additional assessments performed will be included in the individual subject data listings.

For adverse events with missing information for the intensity and causality, the value will not be replaced and will be summarized as a separate category.

c) Blood/plasma/serum data

Any embedded BLQ value (i.e. single BLQ value occurring between 2 quantifiable concentrations) and BLQ values following the last quantifiable concentration in a profile will be set to missing for the purposes of PK analysis.

In a single-dose setting, the BLQ data must be substituted by 0 for concentrations measured before the first quantifiable concentration.

In multiple-dose setting, all BLQ must be set as missing in the dataset.

BLQ values substituted by 0 are included in the PK/NCA calculation whereas missing values are ignored.

In any case, when all concentrations from a concentration-time profile are BLQ, they must be substituted by 0 and included in the PK analysis dataset.

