3.2.4.2 Missing or incomplete dates

In all listings, missing or incomplete dates should be left as they have been recorded. However, for calculation / sorting / assignation based on dates, the following methods will be used:

For partially missing dates for efficacy endpoints derived using tumour assessments, the following imputation rules will be used: if the day of the month is missing, but month and year are known (UN-*MMM-YYYY*), it will be imputed by the 1st of the month (01-*MMM-YYYY*). If this implementation rule produces a date before the first study drug administration, then the date of start of study treatment will be used.

The most conservative approach will be systematically considered (i.e. if the onset date of an AE/concomitant medication is missing / incomplete, it is assumed to have occurred during the study treatment part (i.e. a TEAE for AEs) except if the partial onset date or other data [stop date, ...] indicates differently).

A missing/incomplete date of medical history or disease diagnosis will be assumed to have occurred before any study treatment.

If a partial date and the associated information do not allow to state about the assignment to a group / category, all the possible groups / categories will be considered (i.e.: an AE could be assigned to several possible doses at event onset according to its partial onset date and stop date. Particularly an AE with missing start date will be assigned to each dose received before its end date. Similarly, a medication with partial start and stop dates could be considered as prior and concomitant treatment).

Where this is possible, the derivations based on a partial date will be presented as superior inequalities (i.e.: for an AE started in FEB2004 after the administration performed on 31JAN2004, the days since last dose will be “ ≥ 2 ”, similarly the duration of ongoing AEs or medication will be “ $\geq xx$ ” according to the start and last visit dates).

3.2.4.3 *Outliers*

Any outlier identified prior to database lock which is impossible/improbable will be excluded from the analysis. If any outliers are identified after database lock the statistical analysis should be performed with the actual values and at least one other analysis eliminating or reducing the outlier effect.

The decision of how to handle these outliers will be made during the Data Review Meeting and documented.

[figure not shown]
3.2.5 *Subject disposition*

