3.2.15 Rules and data formats

Data will be presented using an appropriate number of decimal places (i.e. the number of decimal places used does not imply undue precision). Raw data will be presented to the number of decimal places collected, and derived data will be presented to an appropriate number of decimal places. The appropriate number of decimal places will be determined by general practice, mathematical rationale or scientific rationale (e.g. age should be presented in whole numbers).

For summary statistics, the following will be presented n, number of missing values (based on subject who attended the visit), arithmetic mean, standard deviation, median and the range (minimum, maximum).

Mean, median, standard deviation and standard errors of the mean (SE) values will be reported to one decimal place greater than the raw/derived data that they summarise. Minimum and maximum values will be reported with the same precision as the raw data.

Percentages will be reported to one decimal place and 0% will not be presented. Percentages will be calculated using a denominator of non-missing observations. The denominator will be specified in a footnote to the tables for clarification if necessary.

Lower and upper confidence interval values will be presented to one decimal place more than the raw/derived data (i.e., to the same number of decimal places as the mean).

Percentiles (e.g., 25%, 75%) will be presented to one decimal place more than the raw/derived data.

If any, p-values will be reported to four decimal places (e.g.: p=0.0037), after rounding. P-values which are less than 0.0001 will be presented as '<0.0001'.

All values below or above a limit of detection (e.g. <0.1 or >100) will be listed as such.

All text fields must be left justified and numeric or numeric with some text specification (e.g.: not done, unknown, <4.5) must be decimal justified. Dates will be presented in the format [ddmmmyyyy] and times in the format [hh:mm].

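### Duration of response is reported through raw means, medians and crude landmark percentages that treat ongoing responses as finished (SAP 3.2.3 g)

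*SAP*

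**What the plan says.** SAP 3.2.3 g) measures duration of response (DoR) from the first complete or partial response to progression or death, in subjects whose best overall response is CR or PR. For the rest: "If the subject did not have an event of PD or death, then DoR will be the time of last tumor assessment". DoR is listed per subject. The summaries always include summary statistics and "the number and the associated percentage of patients whose DOR is >3, >6, >9 and >12 months", for Part A, Part B and both together. One further result is conditional: "In case of sufficient responders, the median of DOR (calculated based on Kaplan-Meier) and 95% confidence interval of median time will also be summarized". The number that counts as sufficient is not given.

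SAP 3.2.15 sets what these summaries contain. Summary statistics include "arithmetic mean, standard deviation, median and the range (minimum, maximum". For percentages: "Percentages will be calculated using a denominator of non-missing observations". Also: "Percentages will be reported to one decimal place and 0% will not be presented".

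Three neighbouring rules matter:

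- Table 7 in SAP 3.2.3 d) censors at the start of a non-permitted therapy, and the text below it stops central-read follow-up at EOCT/EOAC. Both are written for PFS.
- SAP 3.2.4.1 a) covers missed scans for efficacy endpoints in general ("When tumour assessment visits are completely missing, rules from FDA Guidance") but refers back to the PFS text.
- SAP 3.2.4.2 shows open durations as lower bounds ("similarly the duration of ongoing AEs or medication will be" given with a ≥ sign). It does not mention responses.

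DoR is calculated for both readers (SAP 1.3.2.2). Central reading ends at EOCT/EOAC/EW (SAP 1.3.2).

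**The concern.** A response still ongoing at the last scan has a non-missing value, so nothing in SAP 3.2.15 takes it out. It enters the mean and the raw median as if the response had ended on that day. In the percentages it stays in the denominator and counts as not exceeding every landmark beyond its follow-up. A response already followed past a landmark is counted correctly, so the error runs one way, towards shorter durations.

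The unwritten new-therapy rule can push the other way. A responder who starts a non-permitted therapy is censored for PFS but, as written, goes on accruing DoR.

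At stake is how durable the responses look, above all at the third interim, which includes efficacy (SAP 3.2.17). If responders are too few for the Kaplan-Meier median, the raw figures may be the only summaries shown besides the listing.

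**Working it through.** The plan gives no expected DoR, number of responders or event count, so there is no figure of its own to reproduce. Every median below is an assumption (exponential durations; 12, 18 and 24 months as a range). Months are days / 30.4375.

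**1. The mechanism, on invented data.** Six responders at 4+, 5+, 7+, 10, 13+ and 15 months (+ = ongoing).

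- Raw mean: 54/6 = 9.0. Raw median: (7 + 10)/2 = 8.5. Crude >6 months: 4/6 = 67%. Crude >12 months: 2/6 = 33%.
- Kaplan-Meier: no event before month 10, so 100% at 6 months. At month 10 three are at risk and the curve falls to 2/3, so 67% at 12 months. At month 15 the last one at risk has the event, so the median is 15.

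**2. Third interim, Part B, investigator read.** Inputs:

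- First scan on treatment at week 8: 56 d = 1.84 months. EOCT scan at week 24, 112 d = 3.68 months later (SAP 1.2.1).
- The analysis follows the last EOCT/EOAC/EW (SAP 3.2.17), so a week-8 responder on schedule has at least 3.68 months of follow-up.
- Span from first entry to data cut: 14 months (low end of SAP 1.2.5), up to a bound of 33.08 months. The bound is the 1,007 days from the release of protocol version 6 on 27 February 2018 to the end of November 2020, two years before the planned study end (Protocol, Summary of Changes and Synopsis).

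With uniform entry, follow-up C after response is uniform from 3.68 to span − 1.84, that is to 12.16 or 31.24. If C is independent of duration, the crude percentage beyond t is P(C > t) × S(t), with S(t) = 0.5^(t/median).

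- Short span: P(C > 6, 9, 12) = 6.16/8.48, 3.16/8.48, 0.16/8.48 = 0.73, 0.37, 0.02.
- Long span: 25.24/27.56, 22.24/27.56, 19.24/27.56 = 0.92, 0.81, 0.70.

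| Assumed median | >6 crude (true) | >9 crude (true) | >12 crude (true) |
|---|---|---|---|
| 12 | 51–65% (71%) | 22–48% (59%) | 1–35% (50%) |
| 18 | 58–73% (79%) | 26–57% (71%) | 1–44% (63%) |
| 24 | 61–77% (84%) | 29–62% (77%) | 1–49% (71%) |

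For the 18-month median, the raw median solves P(C > t) × S(t) = 0.5. At t = 6.68 the product is 0.646 × 0.773 = 0.50; at t = 10.55 it is 0.751 × 0.666 = 0.50. So about 6.7 to 10.6 months would be shown against 18. Follow-up is taken as running to the cut; with scans 3 months apart, ongoing durations would be shorter still.

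**3. Final analysis, investigator read, three cycles, complete follow-up.** Eight visits every 3 months start 12 weeks after EOCT (Protocol 5.2.9), so the last scan is 84 d + 21 months = 23.76 months after EOCT. Follow-up is 23.76 months for a response first seen at EOCT and 27.44 for one seen at week 8. All landmarks lie inside this, so the crude percentages are right. So is the raw median, if the true one is below about 24 months. The raw mean is not: with μ = median/ln 2 and p = exp(−C/μ), it equals μ(1 − p).

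| Assumed median | Event-free p | Raw mean | μ | ≥1 of 5 event-free, 1 − (1 − p)^5 |
|---|---|---|---|---|
| 12 | 21–25% | 12.9–13.8 | 17.3 | 68–77% |
| 18 | 35–40% | 15.6–16.9 | 26.0 | 88–92% |
| 24 | 45–50% | 17.2–18.9 | 34.6 | 95–97% |

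**4. Central read.** Longest DoR that scheduled scans can show (no later death counted). Maximum delay means 14-week cycle intervals (8 + 2 + 4) and 5 days at the last visit.

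| Group | On schedule | Maximum delay |
|---|---|---|
| Part A, Follow-up Visit 2 to EOCT | 84 d = 2.8 | 136 d = 4.5 |
| Part B, three cycles | 112 d = 3.7 | 159 d = 5.2 |
| Part B, four cycles | 168 d = 5.5 | 257 d = 8.4 |
| Part B, five cycles | 224 d = 7.4 | 355 d = 11.7 |

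More than 12 months is out of reach for everyone, and more than 6 months for Part A and three-cycle subjects.

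**The case against.** The strongest reply is that censoring is already in the plan. Start, events and end date are all stated, a Kaplan-Meier median cannot be computed without censoring the event-free, and Protocol 11.4 asks for Kaplan-Meier analysis of long-term follow-up data. This stands. It also means that a censoring sentence alone would leave the raw mean, raw median and crude percentages unchanged. But Protocol 11.4 asks for descriptive summaries as well, and the Kaplan-Meier median is an optional extra to figures that are always produced.

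Second, the comparison means in step 3 are extrapolations that no table would report. This stands too. With complete follow-up the raw mean is best read as a mean restricted to the follow-up available; the fault is that it is not labelled so.

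Third, the interim figures rest on an assumed median, uniform entry and a span known only within wide limits. That is so, and the range is wide for that reason. Starting follow-up at zero would give a worse picture, but it does not fit an analysis held after the last EOCT/EOAC/EW unless responders withdraw early.

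Fourth, the central-read point is secondary. SAP 3.2.3 makes the investigator's RECIST assessment primary and central reading a sensitivity analysis, although a sentence in SAP 1.3.2.2 gives central review the larger role. The visit text (Protocol 3.1, SAP 1.2.1) provides the Part A EOCT scan only for subjects enrolled after version 6.0.

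**Conclusion.** The concern holds for the raw summaries. The raw mean is too low whenever any responder is event-free, including at the final analysis. The raw median and the crude percentages are too low where follow-up after response is short: at interim analyses and for dropouts. For Part B at the third interim, under the 18-month assumption, the shortfall is 6–21, 14–45 and 19–62 percentage points at 6, 9 and 12 months (79 − 73 to 79 − 58, and so on).

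Three stronger readings are tempting, and the documents do not support them:

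- That the plan fails to censor DoR. The Kaplan-Meier median implies censoring at the last assessment, and that median does not share the bias described here.
- That all DoR results are biased. Final investigator-read percentages are unbiased with complete follow-up.
- That central tables will show zero durable responses. The schedule makes late landmarks unobservable on central read, but the list of tables is redacted, so whether such cells or footnotes are planned cannot be checked.

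Importance is low. DoR is descriptive, is listed per subject, is not among the listed secondary endpoints (Protocol 3.2.2.4, SAP 3.1.6), and enters no dose or cohort rule (SAP 3.2.18 and 3.2.19).

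**What to change.** In SAP 3.2.3 g):

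- State that DoR runs from first CR/PR to progression or death and is censored at the last evaluable assessment. Apply to it the new-therapy, missed-assessment and central cut-off rules given for PFS with Tables 7 and 8.
- Replace the raw mean, raw median and crude percentages with the Kaplan-Meier median and Kaplan-Meier estimates at 3, 6, 9 and 12 months, with 95% confidence intervals and numbers at risk.
- Say how many responders are sufficient. Below that number, show individual durations with ongoing responses marked as lower bounds, as SAP 3.2.4.2 does for adverse events and medication.
- Label any raw summary that is kept as observed follow-up in response, with the number ongoing.
- If central landmarks are tabulated, name the reader and mark those beyond the last central scan as not estimable.

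The cost is SAP wording and table shells. No new data are needed, since antitumour treatments in long-term follow-up are already recorded (Protocol 6.3.6). The drawback is that landmark estimates will be imprecise, or not estimable, with few responders.

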3.2.4 Missing data and outliers

3.2.4.1 Missing data

a) Efficacy endpoints

When tumour assessment visits are completely missing, rules from FDA Guidance “Clinical Trial Endpoints for the Approval of Cancer Drugs and Biologics” [4] will be implemented as described in section 3.2.3.

Any missing QoL data (EORTC QLQ C30 and QLQ GI.NET21 questionnaires) will be handled as described in section 3.2.3.

b) Safety endpoints

If a value required a retest (for laboratory values, vital signs), the closest non-missing value to the scheduled visit will be used in the summary tables.

If there is a significant number of missing values for a subject (or if there is confirmed data appearing spurious), a decision will be made following consultation with the sponsor regarding the handling of these data in summaries. This decision will be made during the Data Review Meeting and documented.

Any repeat or additional assessments performed will be included in the individual subject data listings.

For adverse events with missing information for the intensity and causality, the value will not be replaced and will be summarized as a separate category.

c) Blood/plasma/serum data

Any embedded BLQ value (i.e. single BLQ value occurring between 2 quantifiable concentrations) and BLQ values following the last quantifiable concentration in a profile will be set to missing for the purposes of PK analysis.

In a single-dose setting, the BLQ data must be substituted by 0 for concentrations measured before the first quantifiable concentration.

In multiple-dose setting, all BLQ must be set as missing in the dataset.

BLQ values substituted by 0 are included in the PK/NCA calculation whereas missing values are ignored.

In any case, when all concentrations from a concentration-time profile are BLQ, they must be substituted by 0 and included in the PK analysis dataset.

3.2.4.2 Missing or incomplete dates

In all listings, missing or incomplete dates should be left as they have been recorded. However, for calculation / sorting / assignation based on dates, the following methods will be used:

For partially missing dates for efficacy endpoints derived using tumour assessments, the following imputation rules will be used: if the day of the month is missing, but month and year are known (UN-*MMM-YYYY*), it will be imputed by the 1st of the month (01-*MMM-YYYY*). If this implementation rule produces a date before the first study drug administration, then the date of start of study treatment will be used.

The most conservative approach will be systematically considered (i.e. if the onset date of an AE/concomitant medication is missing / incomplete, it is assumed to have occurred during the study treatment part (i.e. a TEAE for AEs) except if the partial onset date or other data [stop date, ...] indicates differently).

A missing/incomplete date of medical history or disease diagnosis will be assumed to have occurred before any study treatment.

If a partial date and the associated information do not allow to state about the assignment to a group / category, all the possible groups / categories will be considered (i.e.: an AE could be assigned to several possible doses at event onset according to its partial onset date and stop date. Particularly an AE with missing start date will be assigned to each dose received before its end date. Similarly, a medication with partial start and stop dates could be considered as prior and concomitant treatment).

Where this is possible, the derivations based on a partial date will be presented as superior inequalities (i.e.: for an AE started in FEB2004 after the administration performed on 31JAN2004, the days since last dose will be “ ≥ 2 ”, similarly the duration of ongoing AEs or medication will be “ $\geq xx$ ” according to the start and last visit dates).

3.2.4.3 *Outliers*

Any outlier identified prior to database lock which is impossible/improbable will be excluded from the analysis. If any outliers are identified after database lock the statistical analysis should be performed with the actual values and at least one other analysis eliminating or reducing the outlier effect.

The decision of how to handle these outliers will be made during the Data Review Meeting and documented.

[figure not shown]
3.2.5 *Subject disposition*

A listing of dates of assessments (relative day), including EOCT, EOAC (part B only) and End of Long-term Follow-up (EOLTFU) dates and their study exposure will be presented by subject for each study part, cohort (part B only) and radioactivity level adapted or not (part B only). Subject disposition information will be presented using the eligible subject set.

A summary table will be presented for each subject population presenting the number of subjects in each study part and cohort (part B only) at each assessment and identifying the number of subjects who withdrew over time. The reasons for exclusions from each of the populations will be listed and tabulated.

A listing of any deviations due to COVID-19 will be generated separately and a table summarizing Deviations due to COVID-19 will be produced.

The number of patients exposed to COVID-19 as well as impacted or infected (see definition below) will also be presented.

The number of visits impacted due to COVID-19 with the reasons will be summarized to assess the impact of COVID-19

A summary table will present the number of subjects who received study treatment, extent of subject exposure in the study and the study drug exposure for each study part and cohort (part B only).

The definition of the extent of subject exposure is the time interval between the first informed consent signed to the EOCT, EOAC (Part B) or EW visit completed (c.f. in [Appendix 1: Derived Data](#)). The definition of Study drug exposure (days) is the time interval between last drug intake - date of first drug intake +1 (c.f. in [Appendix 1: Derived Data](#)).

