2.1.2 Per Protocol Set (PP)

The Per-Protocol Set (PP) consists of all subjects in the ITT Set who complete the study according to the protocol with no major protocol deviation. Any protocol deviation will be evaluated by the Sponsor based on the individual case. Major protocol deviations will be defined in the Protocol Deviations Document and identified in a data review meeting before database lock.

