2.5 Primary Analysis Set

The primary analysis based on the assessment of the safety and tolerability of the study drug (primary objective) will be performed on the Safety Analysis Set (SAS).

The efficacy analysis will be performed on the ITT and PP sets.

Patients will be assigned to each analysis set prior to the statistical analysis.

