3.1.1 Primary safety endpoint(s)

Frequencies and/or descriptive summaries of standard safety and tolerability parameters: AEs (including SAEs) according to National Cancer Institute (NCI) Common Terminology Criteria for Adverse Events (CTCAE) v5.0 and vital signs, laboratory tests (haematology, biochemistry and urinalysis, and pituitary markers), 12-lead and Holter electrocardiogram (ECG), DLTs, physical examination results and use of concomitant medication throughout the study.

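### The pre-lock outlier rule excludes values that are merely improbable, with no confirmation of error and no analysis that keeps them

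*SAP*

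**What the plan says.** SAP section 3.2.4.3 (Outliers) has two rules, separated by database lock. Before lock: "Any outlier identified prior to database lock which is impossible/improbable will be excluded from the analysis". After lock: "If any outliers are identified after database lock the statistical analysis should be performed with the actual values and at least one other analysis", the second analysis being one aimed at "at least one other analysis eliminating or reducing the outlier effect". The section closes with a procedural step: "The decision of how to handle these outliers will be made during the Data Review Meeting and documented".

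Neither *outlier* nor *improbable* is defined. The section gives no threshold, does not ask for a source check before exclusion, and does not exempt safety data. Its parent section, 3.2.4, covers safety endpoints expressly. Section 3.2.4.1(b) provides for a consulted, documented decision where a subject has many missing values or "if there is confirmed data appearing spurious", but it does not limit the outlier rule.

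The primary endpoint in SAP section 3.1.1 is "Frequencies and/or descriptive summaries of standard safety and tolerability parameters". It includes laboratory tests, vital signs and ECG as well as adverse events and DLTs.

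**The concern.** An impossible value is an error and should go. An improbable value may be true, and in a first-phase radiopharmaceutical trial the unusual reading is often the one of interest. Protocol section 1.4 reports that, with the same compound, four of seven subjects given a second cycle had Grade 4 haematological toxicity. Real extremes are therefore to be expected here.

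The slash in the pre-lock rule makes improbability sufficient on its own. A true value can be left out of the main analysis, and the report need not show what the table would have looked like with it. The same value noticed a week after lock would stay in. What is at stake is whether the summary tables of the primary safety endpoint, and the dosimetry tables, reflect the data collected.

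**Working it through.** No sample size, power or other design figure in the plan depends on this rule, so there is no stated figure to reproduce. The check sets the passages side by side and then sizes the effect.

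**1. The two rules compared (SAP 3.2.4.3)**

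| | Found before lock | Found after lock |
|---|---|---|
| Trigger | outlier judged impossible or improbable | any outlier |
| Main analysis | value left out | actual value used |
| Second analysis | none required | at least one |
| Confirmation as an error | not required | not needed, since the value is kept |
| Definition or threshold | none | none |

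**2. How the plan treats comparable data elsewhere.** For OPS201 concentrations, protocol section 11.4.5 has suspicious values looked into and retained where possible, with every exclusion explained in the report. SAP 3.2.4.1(b) ties special handling of odd safety values to their being confirmed. Section 3.2.4.3 has neither feature.

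**3. Which summaries depend on the extreme value**
- Nadir and day to nadir by cycle (SAP 3.2.1.3; Appendix 1, item 18).
- Shift from baseline to worst CTCAE grade for haemoglobin, neutrophils and platelets (SAP 3.2.1.3).
- Minimum and maximum in the standard summaries (SAP 3.2.15).
- Geometric mean and geometric CV of absorbed dose, and between-visit dose ratios (SAP 3.2.2).

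**4. Size, taking one isolated reading as excluded**

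Cohorts 1, 2, 4, 5, 7 and 8 enrol 3 to 5 subjects; Cohorts 3 and 6 enrol 8 to 10 (SAP 1.2.1.2).

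*Laboratory readings.* Haematology is taken predose and on Days 2, 3, 4–5, 7–8 and 15 (protocol 8.2.1), which is 6 readings. The Part B schedule adds Days 29 and 42, giving about 6 + 2 = 8 per subject per cycle. In a cohort of three that is 3 × 8 = 24 readings per cycle, so one reading is 1/24 = 4.2% of them. The subject stays in the table.

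*Nadir.* With the lowest reading gone, that subject's nadir becomes the second-lowest. The cohort mean nadir then rises by (second-lowest − lowest)/n: one third of the gap for n = 3, one fifth for n = 5, one tenth for n = 10. The documents give no figure for the gap.

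*Worst grade.* The table changes only if no other post-baseline reading from that subject reaches the same grade. When that condition holds, one subject moves category, which is 1/n: 33.3 points for n = 3, 20.0 for n = 5, 12.5 for n = 8 and 10.0 for n = 10.

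*Organ dose.* Specific absorbed dose per organ is computed once per administration (SAP 3.1.3). Excluding it leaves n − 1 subjects in that organ-and-cycle cell; the subject's other organs and cycles are untouched.

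**The case against.** The strongest reply is that the rule is narrower in practice than on paper, and much of that stands.

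- All safety data remain in the listings (SAP 3.2.1). Grade 3 and 4 haematological toxicities have their own listings, and key laboratory values are plotted by subject (SAP 3.2.1.3).
- Adverse events and DLTs come from investigator reports, not from screening numbers. A laboratory abnormality that changes dosing or is clinically significant should be reported as an adverse event (protocol 8.1.2.4).
- Serial sampling would normally corroborate or refute a single odd count. A severe platelet fall is anticipated with this compound and might not be called improbable at all.
- The protocol requires 100% source data verification (13.3) and queries on unexplained items (13.6), so much of the confirmation step already exists operationally.
- Handling is decided and documented at the Data Review Meeting. SAP 2.1.2 refers to protocol deviations being "identified in a data review meeting before database lock"; if this is the same meeting, it falls before lock.

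These points limit the harm but do not repair the rule. Listings do not put a value back into a nadir, worst-grade or geometric-mean table. Source verification is not made a condition of exclusion. The meeting supplies a record but no criterion, and its discretion sits awkwardly with a rule that says the value will be excluded. Only some laboratory abnormalities become adverse events.

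A reader might also infer that the pre-lock rule is the more open to bias because staff then know the cohort. The documents do not support that: the study is open-label, so cohort is known before and after lock. The difference that matters is that only pre-lock exclusions lack an analysis with the value kept.

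**Conclusion.** The rule as written is faulty and should be corrected. It permits a true extreme laboratory, vital-sign, ECG or dosimetry value to leave the summary tables because it looks unlikely, with no confirmation and no parallel analysis, and it contradicts the treatment of the same value found after lock. The effect on any one table depends on the isolated reading and on cohort size, as shown above; no general magnitude can be given. The conclusion assumes that section 3.2.4.3 is followed literally. If the sponsor means only data errors, the text should say so.

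Three stronger readings are tempting and do not hold:
- **Real toxicities vanish from the trial record.** They do not: listings, adverse event reports and DLT counts remain.
- **One exclusion in a three-subject cohort removes a third of the data.** The rule excludes a value, not a subject. For serial laboratory data n stays at 3, and even an excluded organ dose affects only one cell.
- **Dose escalation would be distorted.** The data sets for the SRC and DRB are set by charter (SAP 3.2.17), and nothing in the documents shows this outlier rule reaching them.

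**What to change.** Replace the pre-lock sentence in SAP 3.2.4.3 with a rule that applies whenever the outlier is found:

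- Exclude only values confirmed by source query as impossible or erroneous.
- Keep improbable but unrefuted values in the main analysis, with a sensitivity analysis without them.
- List every excluded value with its reason, as protocol section 11.4.5 already requires in substance for PK concentrations.

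The Data Review Meeting can stay as the place where decisions are recorded, now with a criterion to apply. The change extends to all data what the plan already does after lock and for PK. The cost is a short change of text and an occasional extra sensitivity table.
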